
5.1.3 Exploratory Endpoints

Alcohol consumption will be assessed with Time-line Follow-back (TLFB) [115] and percent carbohydrate-deficient transferrin (CDT) in serum. History of trauma will be assessed with the Trauma History Questionnaire (THQ) [116] at baseline.

6 Study Enrollment and Withdrawal

6.1 Inclusion Criteria

In order to be eligible to participate in this study, an individual must meet all of the following criteria:

- 1) Males and females age 18-65
- 2) DSM-5 diagnosis of moderate or severe AUD
- 3) Able to provide voluntary informed consent
- 4) At least 6 heavy drinking days (4 or more drinks for a woman, 5 or more drinks for a man) in the 30 days prior to screen
- 6) If of childbearing potential (male or female), are willing to use approved form of contraception from screening for duration of the trial
- 7) Able to provide at least two locators
- 8) Endorse desire to cut down or stop drinking
- 9) Agrees to abstain from all other cannabinoid use for duration of the study

CONFIDENTIAL

This material is the property of the NYU School of Medicine and Langone Health
Do not disclose or use except as authorized in writing by the study sponsor

6.2 Exclusion Criteria

An individual who meets any of the following criteria will be excluded from participation in this study:

- 1) Current alcohol withdrawal (CIWA-Ar score >7)
- 2) Exclusionary medical conditions (e.g. current severe alcohol withdrawal requiring medical hospitalization, significantly impaired liver function, Type I Diabetes)
- 3) DSM-5 diagnosis of schizophrenia, schizoaffective disorder, bipolar disorder
- 4) High risk of adverse emotional or behavioral reaction based on investigator's clinical evaluation (e.g., evidence of serious personality disorder, antisocial behavior, serious current stressors, lack of meaningful social support)
- 5) Current significant suicidality (assessed using the C-SSRS), any suicidal behavior in the past 12 months, or any history of serious suicide attempts requiring hospitalization, or current significant homicidality
- 6) History of severe Traumatic Brain Injury (LOC > 24 hours)
- 7) DSM-5 diagnosis of current mild cannabis use disorder and/or moderate or severe substance use disorder for a substance other than alcohol or nicotine
- 8) Significant laboratory abnormalities, including significantly impaired liver function*, serious abnormalities of complete blood count or metabolic panel
- 9) Active legal problems likely to result in incarceration within 12 weeks of treatment initiation
- 10) Pregnancy or lactation
- 11) Current use of exclusionary medications, including cannabinoids; treatments for addictions including alcohol; moderate to strong inhibitors of CYP3A4 or CYP2C19; medications metabolized primarily by CYP3A5, or CYP3A7; and medications with a narrow therapeutic index which are substrates of CYP3A4, UGT1A9, UGT2B7, CYP2C8, CYP2C9, CYP2C19, CYP1A2, or CYP2B6.
- 12) Allergy to any ingredient of the study compound.
- 13) Current treatment for AUD, with exception of AA/12-step treatment
- 14) No inpatient psychiatric treatment in the last 12 months, with the exception of detox and extended Emergency Department stays
- 15) A positive urine drug screen for THC, cocaine and/or opioids at screen

*Significantly impaired liver function will be operationalized as alanine aminotransferase (ALT), aspartate aminotransferase (AST), or alkaline phosphatase (Alk Phos) $> 2.5 \times$ upper limit of normal (ULN), or Total bilirubin $> 2.0 \times$ ULN in the absence of Gilbert's syndrome.

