6.6 Participant Withdrawal or Termination

6.6.1 Reasons for Withdrawal or Termination

Participants are free to withdraw from participation in the study at any time upon request. An investigator may terminate participation in the study if:

- Any clinical adverse event (AE), laboratory abnormality, or other medical condition or situation occurs such that continued participation in the study would not be in the best interest of the participant
- The participant meets an exclusion criterion (either newly developed or not previously recognized) that precludes further study participation
- The participant fails to adhere to protocol requirements

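### Exclusion 14 is worded as an inclusion condition, so under its lead-in it reads the wrong way round: a drafting inversion to correct, with probably little practical effect

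*Combined protocol and SAP*

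**What the plan says.** The protocol's section 6.2 opens with the rule "An individual who meets any of the following criteria will be excluded from participation in this study". Item 14 under that rule is "No inpatient psychiatric treatment in the last 12 months, with the exception of detox and extended Emergency Department stays".

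The items on either side are worded positively. Item 13 is "Current treatment for AUD, with exception of AA/12-step treatment" and item 15 is "A positive urine drug screen for THC, cocaine and/or opioids at screen".

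The list in section 6.1 works the other way: "In order to be eligible to participate in this study, an individual must meet all of the following criteria". It has no item on inpatient psychiatric treatment.

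Section 6.6.1 uses the exclusion criteria again after enrolment. One of its grounds on which an investigator may end participation is "The participant meets an exclusion criterion (either newly developed or not previously recognized) that precludes further study participation".

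**The concern.** An exclusion list works only if every item describes someone to be kept out. Item 14 describes someone to be let in. Joined to its lead-in, it reverses the rule: absence of a recent psychiatric admission becomes the reason for exclusion.

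This is operative eligibility text, and other parts of the plan depend on it. Section 6.3 describes a scripted pre-screening form that asks about the criteria, a check of initial eligibility in the electronic health record, and a data-service search for patients who may qualify. The schedule of assessments following section 7.3.2 lists an eligibility checklist at screening. A form, checklist or search built word for word from item 14 would carry the wrong polarity. Section 25.3 treats any departure from the protocol as a deviation to be reported to the funder's program official and, under the local board's guidelines, to the IRB. The literal wording therefore leaves an avoidable opening for audit queries.

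**Working it through.** No arithmetic applies. The check is one of logic, in four steps.

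**1. Apply the lead-in to item 14.** The inputs are the section 6.2 rule (any item met means excluded) and the wording of item 14. The last column shows the result if the word No is deleted.

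| History in the last 12 months | Item 14 met as written? | Result of item 14 as written | Result with No deleted |
|---|---|---|---|
| No inpatient psychiatric treatment | Yes | Excluded | Not excluded |
| Only detox or extended emergency stays | Yes, if the carve-out is read as part of the condition | Excluded | Not excluded |
| Other inpatient psychiatric treatment | No | Not excluded by this item | Excluded |

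Every row reverses. The second row depends on how the carve-out is parsed; the first and third do not.

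**2. Compare polarity across the list.** There are 15 items. Items 1 to 13 and item 15 (15 − 1 = 14 items) each name a condition, history, treatment or test result whose presence excludes. Item 14 alone names an absence. Item 13 shows the same construction done correctly: a positive statement followed by an exception.

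**3. Look for a correction elsewhere.** Section 6.1 has no matching item. The screening steps in section 8.3.1 refer to the criteria without restating them. No other section repeats the rule in either polarity, so nothing overrides the wording of item 14.

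**4. Test whether a looser sense of meeting a criterion rescues the text.** Section 6.3 lets candidates proceed as long as the inclusion and exclusion criteria are still met, using the verb to mean satisfied. In that sense item 14 reads correctly, but the other fourteen exclusions would then be inverted. No single sense of the verb works for all 15 items, so the reader has to settle the direction item by item.

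**The case against.** The best answer is that the sentence explains itself. An exception for detox and extended emergency stays has a purpose only if inpatient treatment is what excludes. The literal reading would confine a trial recruited from the general public by local advertising (section 6.3) to people with a psychiatric admission in the past year, which nobody could take as intended. The trial has one center, pre-screening follows an IRB-approved script, and licensed providers carry out a full psychiatric evaluation. The wording of the script is not in the documents, so nothing shows that the slip reached a working tool. All of this stands, and it limits the importance of the point. It does not remove the conflict between item 14 and its lead-in, which remains in the current text.

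Two stronger readings are tempting, and the documents support neither.

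- **A reader might infer that the trial admits people with recent psychiatric admissions.** The text shows only that item 14 does not exclude them. Item 3 (schizophrenia, schizoaffective disorder and bipolar disorder), item 4 (the investigator's judgment of high risk) and item 5 (suicidality, and serious homicidality) may still do so.
- **A reader might infer that most enrolled participants are eligibility deviations.** That needs the proportion of participants without a recent admission, which the documents do not give. It also needs an auditor to adopt a reading that item 14's own exception argues against.

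**Conclusion.** Item 14 is wrong as written, and the severity is minor. It is a drafting error, not a choice about whom to study.

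The finding that the wording is inverted rests only on the text of section 6.2. The judgment that the practical effect is probably small rests on an assumption: that staff read item 14 in line with its exception and with the rest of the list. The documents make that likely but do not confirm it, because neither the pre-screening form nor the content of the checklist is included. The number of candidates affected cannot be estimated from what is given. No endpoint, analysis, alpha level, power statement or sample size changes.

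**What to change.** Bring item 14 into line with its lead-in by one of two equivalent edits:

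- delete the word No from item 14 and leave it in section 6.2; or
- move the sentence unchanged to section 6.1, where a negative condition reads correctly.

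Both give the rule that the sentence's own exception implies. Then confirm that the scripted pre-screening form, any record search built from the criteria, and the inclusion/exclusion checklist carry the same polarity.

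The cost is a one-word or one-line amendment and a short check of those tools. No data collection or analysis is affected.

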6.3 Strategies for Recruitment and Retention

Subjects will be approximately 60 women and men, age 18 or greater, with moderate to severe AUD, recruited from the public through local media advertisements, 40 of whom will be randomized and complete the treatment portion of the study. Participants will be recruited between approximately September 2019 and August 2021. Informed consent will be given at NYU SoM space occupied by the PI within Bellevue Hospital in New York, NY, following an initial telephone consent and screen to determine potential eligibility for the study. Participants will be asked to share information about their drinking and use of any other drugs, anxiety and mood, and undergo a full medical and psychiatric evaluation at screen by licensed providers. Participants will have the option of completing the initial portion of the screening visit remotely. In this case, participants will be asked to share information about their drinking and use of any other drugs, anxiety and mood, and undergo a full psychiatric evaluation by licensed providers remotely via Webex. If inclusion and exclusion criteria continue to be met following the remote portion of the screening visit, participants will be invited to undergo a full in-person medical evaluation by licensed providers to complete the screening visit.

Active recruitment will also take place through social media sources, including Facebook and Twitter, at social service agencies, community mental health clinics, community organizations, local professional organizations, residential treatment facilities, consenting support and recovery centers, regional employee assistance programs, religious organizations, cultural centers, social clubs, and local universities. Recruitment materials will also be posted to the laboratory's website (centerforpsychedelicmedicine.com).

Clinicians will provide study staff with names and contact info for interested patients, who will sign an

CONFIDENTIAL

This material is the property of the NYU School of Medicine and Langone Health
Do not disclose or use except as authorized in writing by the study sponsor

authorization form allowing the clinic to release only their contact information to study staff (no clinical or diagnostic information will be shared). Once referrals are given, the study team will access EPIC to determine the participant's initial eligibility. Subjects will also be recruited through advertisements in local newspapers. Additionally, the study team will use NYU's DataCore service to gather information from EPIC for current NYU patients who may be eligible.

Active recruitment will also take place through social media sources, including Facebook, ResearchMatch, Craigslist, and Instagram, at social service agencies, community mental health clinics, community organizations, local professional organizations, residential treatment facilities, consenting support and recovery centers, regional employee assistance programs, religious organizations, cultural centers, social clubs, and local universities.

Potential participants contacted through any of the above channels will be asked to complete a brief pre-screening interview either in person or by telephone, using an IRB approved, and scripted pre-screening form describing the basic facts of the study and inquiring about inclusion and exclusion criteria. Participants who pass the pre-screening interview (i.e., those who appear likely to qualify for the study and remain interested in participating) will be scheduled for an in-person screening visit or for the remote portion of the screening visit, followed by the remaining in-person portion of the screening visit, if inclusion and exclusion criteria continue to be met.

6.4 Duration of Study Participation

Including screening and follow-up visits, the total duration of participant involvement will be approximately 12 weeks. Total time of contact during these 12 weeks is estimated at 28 hrs.

6.5 Total Number of Participants and Sites

Recruitment will end when approximately 60 participants are enrolled. It is expected that approximately 60 participants will be enrolled in order to produce 40 randomized participants.

6.6 Participant Withdrawal or Termination

6.6.1 Reasons for Withdrawal or Termination

Participants are free to withdraw from participation in the study at any time upon request. An investigator may terminate participation in the study if:

- Any clinical adverse event (AE), laboratory abnormality, or other medical condition or situation occurs such that continued participation in the study would not be in the best interest of the participant
- The participant meets an exclusion criterion (either newly developed or not previously recognized) that precludes further study participation
- The participant fails to adhere to protocol requirements

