6.6.2 Handling of Participant Withdrawals or Termination

Every effort will be made to undertake the protocol-specified safety follow-up procedures to capture AEs, SAEs, and UPs. The investigator will attempt to obtain at a minimum survival data on all participants lost to follow-up. If a participant is lost to follow-up, the study team will attempt to contact the participant 3 times by telephone and twice by email. If the participant fails to respond, locators identified by the participant at screening will be contacted in the method specified by the participant. If participants withdraw, are terminated, or are lost to follow-up prior to the end of the 8-week treatment phase (prior to T7), they will not be replaced to allow for 40 participants to complete the 8-week treatment phase (through T7), and their partial data will be handled according to the statistical analysis plan (SAP).

CONFIDENTIAL

This material is the property of the NYU School of Medicine and Langone Health
Do not disclose or use except as authorized in writing by the study sponsor

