8.4 Concomitant Medications, Treatments, and Procedures

All concomitant prescription medications taken during study participation will be recorded on the case report forms (CRFs). For this protocol, a prescription medication is defined as a medication that can be prescribed only by a properly authorized/licensed clinician. Medications to be reported in the CRF are concomitant prescription medications, over-the-counter medications and non-prescription medications.

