16.4 Pregnancy Reporting

Pregnancy information on clinical study subjects is collected by the investigator. If a subject should become pregnant during the course of the study, the investigator or qualified designee will contact the IRB within 5 working days of the PI or qualified designee first becoming aware of the pregnancy.

Tilray Pregnancy Reporting Requirements: Every exposure during pregnancy (participant) should be reported on a Tilray SAE worksheet within 24 hours of the site becoming aware of the pregnancy as a case of special interest from the time of study enrollment to the end of study participation. If an SAE occurs in conjunction with the pregnancy, then the Tilray reporting timeframe for an SAE (24 hours) must be met. In the event of a pregnancy, administration of study medication will be discontinued, but all other follow-up data, including safety data, will be collected.

Pregnancies resulting in congenital abnormalities or birth defects in offspring meet the requirements for an SAE and will be collected, documented, and reported according to the procedures outlined above for SAEs.

17 Reporting of Investigational Medicinal Product Quality Complaints

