21.2 Statistical Hypotheses

Hypothesis 1a: Within-group circulating CBD levels will stabilize within one week, i.e. pre-CBD dosing (12 hour) levels obtained after 1 week of treatment will not differ from those obtained after 4 weeks of treatment at each dose.

Hypothesis 1b: Circulating CBD levels obtained at the 1200 mg/day dose will be comparable to those associated with anti-additive effects in animal models, i.e., in the range of 200-400 ng/ml.

Hypothesis 1c: No clinically significant cognitive or motoric impairments, CBD-related serious adverse events, or persisting adverse effects will be observed.

Hypothesis 2a: Relative to placebo, CBD will improve self-report measures of craving, anxiety, mood, and self-efficacy.

Hypothesis 2b: Relative to placebo, CBD will be associated with decreased stress- and alcohol cue-induced craving and physiological stress response

Hypothesis E: Relative to the placebo-treated group, CBD-treated participants will have fewer heavy drinking days during and for four weeks after treatment with 1200mg/day CBD vs. placebo.

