21.3.3 Analysis of the Secondary Endpoint(s)

For Hypothesis 2a, between- and within- group differences on measures of craving, anxiety, depression, and self-efficacy (T1, T3, T4, T6, T7, T8) will be evaluated. For Hypothesis 2b, linear mixed effects models will be constructed as described by [name] et al. [123] with treatment group (CBD vs. placebo) included as a fixed

CONFIDENTIAL

This material is the property of the NYU School of Medicine and Langone Health
Do not disclose or use except as authorized in writing by the study sponsor

between-subjects factor, time (nested factor including pre-imagery, imagery, and recovery periods at both T3 and T6) and script type (stress, alcohol cue, neutral) as fixed within-subjects factors, with subject as a random effect. Between- and within- group comparisons and interactions for measures of craving, anxiety, and physiological stress response will be assessed.

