21.3.10 Exploratory Analyses

Hypothesis E will be assessed by comparing within- and between- group differences in percent heavy drinking days from baseline (T1) to week 8 of treatment with study medication (T7) and during the 4-week period following administration of study medication (T8-T9)

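### After an investigator ends participation (6.6.1), only safety follow-up is promised (6.6.2), so later drinking and mood data need not be collected, and 7.1.9 drops these participants from the primary safety comparison

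*Combined protocol and SAP*

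**What the plan says.** Section 6.6.1 gives the investigator discretion to end a participant's place in the study on three grounds: an adverse event, laboratory abnormality or other medical situation; a newly met exclusion criterion; or failure to adhere to the protocol. The second ground reads "The participant meets an exclusion criterion (either newly developed or not previously recognized) that precludes further study participation".

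Section 6.6.2 covers every kind of early exit in the same way. Its commitment is that "Every effort will be made to undertake the protocol-specified safety follow-up procedures to capture AEs, SAEs, and UPs", with at least survival status sought for those lost to follow-up. Participants who leave before T7 are not replaced, and their partial data are left to a SAP that 21.1 says is still to be written.

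Pregnancy, itself exclusion criterion 10, is treated differently. Section 16.4 says that "administration of study medication will be discontinued, but all other follow-up data, including safety data, will be collected".

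The outcomes affected run well past mid-treatment. Section 21.3.3 says that "measures of craving, anxiety, depression, and self-efficacy (T1, T3, T4, T6, T7, T8) will be evaluated". Section 21.3.10 compares "percent heavy drinking days from baseline (T1) to week 8 of treatment with study medication (T7") and also covers the four weeks after study medication. Section 7.1.9 admits only participants who complete treatment through T7 to the primary analyses.

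**The concern.** Several exclusion criteria in 6.2 can arise during the trial because of drinking or study drug: criterion 13 ("Current treatment for AUD, with exception of AA/12-step treatment"), addiction medication (11), alcohol withdrawal (1), and liver tests above 2.5 times the upper limit of normal (8). If participation ends for such a reason, the missing later outcomes may differ systematically from those observed, and perhaps differently by arm. The SAP can model missing data but cannot supply data that were never collected. Section 8.4 records concomitant medication only while the participant is in the study, so AUD medication begun after termination need not appear either.

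The completer rule in 7.1.9 adds a separate problem. A participant taken out because of an adverse event before T7 is excluded from the analysis meant to compare adverse events between arms.

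At stake are the secondary comparison (2a), the exploratory drinking comparison (E) and the primary safety comparison (1c).

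**Working it through.** **1. What must be collected after termination**

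| Section | Drug stopped | Outcome data required afterwards |
|---|---|---|
| 6.6.1 and 6.6.2 (any termination) | yes, with participation | adverse events; survival status if lost |
| 7.1.8 (significant risk) | yes | not stated |
| 13 (adverse events) | may be | clinical and laboratory checks until resolution |
| 16.4 (pregnancy) | yes | all other follow-up data |

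Only 16.4 secures TLFB, PACS, BAI, BDI-II and AASE. Even for adverse events the duration is unsettled, because section 11 ends recording 7 days (30 for serious events) after the last day of participation.

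**2. What one termination can lose.** Take a participant terminated just after T4, when the first on-treatment liver tests are drawn.
- Drinking: weeks 5-12. That is 4 of the 8 treatment weeks in 21.3.10 and all 4 post-treatment weeks. Weeks 1-4 are kept.
- Hypothesis 2a: T6, T7 and T8, which is 3 of 5 post-baseline visits (T3, T4, T6, T7, T8).
- Hypothesis E as worded in 21.2, that "CBD-treated participants will have fewer heavy drinking days during and for four weeks after treatment with 1200mg/day CBD vs. placebo": this whole window.

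**3. Illustration of size.** The protocol gives no termination rate, so every rate and correlation here is an assumption. The 0.6 SD difference is the effect size that 21.4 names for Hypothesis E, used only as a scale.

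Let later drinking be standardised within arm, and let liability to termination correlate r with it. Participants above a cut-off leave, under the same rule in both arms. With φ and Φ the standard normal density and distribution function:
- h(c) = φ(c)/Φ(c); c is the normal quantile at 1 − placebo rate; the CBD cut-off is c′ = c + 0.6r.
- Retained difference = 0.6 − r[h(c) − h(c′)].
- Retained variance per arm = 1 − r²h(c)[c + h(c)], using c′ for CBD.
- Observed-SD difference = retained difference / √(mean of the two variances).

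Example with placebo rate 20% and r = 0.7: c = 0.842, h(c) = 0.350, c′ = 1.262, h(c′) = 0.201. The difference is 0.6 − 0.7 × (0.350 − 0.201) = 0.496. The variances are 0.796 and 0.856, and the square root of their mean is 0.909. The result is 0.496/0.909 = 0.545, a shrinkage of 9%.

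Difference in observed SD (true value 0.6):

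| Placebo terminated | r = 0.3 | r = 0.7 | r = 0.9 |
|---|---|---|---|
| 5% (1 of 20) | 0.595 | 0.579 | 0.568 |
| 10% | 0.593 | 0.565 | 0.546 |
| 20% | 0.589 | 0.545 | 0.512 |
| 30% | 0.587 | 0.530 | 0.484 |

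Shrinkage is therefore 1-5% at the 5% rate and at most 19% at 30%. In SD units of the full, unselected population it is 1.5-11% and at most 35%.

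Modelling baseline and weeks 1-4 data reduces the loss. A simulation (400,000 per arm, r = 0.7, assumed between-period correlation 0.6, assumed 0.3 SD effect in weeks 1-4) gives 0.589, 0.577 and 0.570 at 10%, 20% and 30%, a shrinkage of 2-5%.

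**4. No true effect.** Under a common rule and no effect, the expected bias is zero. A spurious difference needs different termination rates by arm. Assuming 4 of 20 placebo and 1 of 20 CBD participants leave, with r = 0.7: 0.7 × (0.350 − 0.109) = 0.169; the variances are 0.796 and 0.907; 0.169/0.923 = 0.183 observed SD (0.073 at r = 0.3, 0.250 at r = 0.9; 0.112 with earlier data modelled at r = 0.7). The standard error with 20 per arm is √(2/20) = 0.316, so 0.183 is rather more than half of one standard error. Reversing the rates reverses the sign.

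**The case against.** Termination is discretionary, and the exclusion-criterion ground applies only where the criterion rules out continuing. The protocol can stop drug alone (7.1.8, 13), the PI may approve otherwise prohibited medication (8.5), and 21.3.5 counts stopping the intervention separately from stopping follow-up. These points stand and reduce how often the gap would matter. None of them requires outcome data afterwards.

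It is also fair that 6.6.2 treats all exits alike, so a remedy tied to exclusion criteria alone would fail: the same participant could leave on the adverse event or non-adherence ground. Nor should follow-up be unconditional. Ending contact may be right in acute suicidality or hospitalisation, and impossible in incarceration. The remedy below allows for both.

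Three stronger inferences are tempting.
- A reader might infer that the protocol forbids outcome collection after termination. It is silent, which is different.
- A reader might infer that safety information is lost. Section 6.6.2 collects adverse events and 16.1 sends them to the DSMB and FDA; what 7.1.9 affects is the planned between-arm comparison.
- A reader might infer that cognitive testing certainly stops. Section 3.3 counts cognitive and motoric function among safety measures, so the text is ambiguous.

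**Conclusion.** The gap is real and worth closing, but it does not invalidate the trial. Outside pregnancy, an investigator-initiated termination leaves later drinking, craving, anxiety, mood and self-efficacy data uncollected unless someone chooses to collect them. As 7.1.9 stands, it also takes the participant out of the Hypothesis 1c comparison. The loss may be informative for Hypotheses 2a and E.

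Its size cannot be computed from the protocol, and its direction is unknown: drinking-driven exits could shrink a true benefit, while liver-driven exits could concentrate in the CBD arm, which the illustration does not represent. The figures above are illustrative only, and the no-effect example rests on unequal termination rates that nothing in the protocol predicts. A small to moderate effect is the reasonable expectation, on secondary and exploratory outcomes in a 40-participant proof-of-concept trial. It is a point to consider, held with medium confidence.

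**What to change.** In 6.6.2, extend the 16.4 rule to all investigator-initiated terminations. Stop study drug as needed, but continue follow-up unless consent is withdrawn, the investigator judges contact clinically inappropriate, or contact is not feasible. Specifically:
- Collect TLFB and adverse events at the remaining scheduled times, by telephone if needed (T9 already is).
- Collect PACS, BAI, BDI-II and AASE where visits are attended. Do not require the cue/stress task.
- Record the reason and date of termination, and the start date of any AUD treatment, including treatment begun after study drug stops.

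In 7.1.9, lift the T7-completer restriction for the Hypothesis 1c safety comparisons, so that all randomised participants who took study drug count. Report on-drug and off-drug observations separately, so that off-drug time does not dilute a harm signal. Keep Hypotheses 1a and 1b to samples taken on the assigned dose.

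The cost is a few sentences, some staff time, and visit payments. At the 26.3 rates, T6, T7 and T8 come to $60 + $40 + $40 = $140 for a participant terminated at T4 who attends all three. The scientific drawback is that later drinking data may reflect non-study AUD treatment, which could narrow the difference between arms; the recorded start dates make that visible.
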